4.4.2.2.1 Statistical Hypothesis, Model and Method of Analysis

The following null and alternative hypotheses will be evaluated:

- H_0 : There is no difference in the mean MGI score at 4 weeks between the Test product and Reference product.
- H_1 : There is a difference in the mean MGI score at 4 weeks between the Test product and Reference product.

Mean MGI at Week 4 will be analyzed as described for the primary analysis (Section 4.4.1.2), using the Baseline MGI value as covariate. The adjusted means and SEs of the two product groups together with the product difference, SE, 95% CI of the difference and p-value will be provided in Table 14.2.4.2.1 for the mITT population. The % adjusted mean difference will also be presented.

4.4.2.3 Mean Turesky Plaque Index (TPI) [Overall and Interproximal] at Week 4

The Overall TPI score for each subject at each visit will be calculated as the average index value over all evaluable tooth sites scored as follows:

- Overall TPI Score = Sum of index values over all evaluable tooth sites/Number of evaluable tooth sites.

The Interproximal TPI score for each subject at each visit will be calculated as the average index value over all interproximal tooth sites (distal and mesial) scored as follows:

- Interproximal TPI Score = Sum of index values over all evaluable interproximal tooth sites (distal and mesial) /Number of evaluable interproximal tooth sites (distal and mesial).

The evaluable tooth sites are those scored as 0, 1, 2, 3, 4 or 5.

The Overall TPI score and Interproximal TPI score have a range of 0 to 5.

TPI will be assessed for all evaluable surfaces of the facial and lingual surfaces of the teeth (7-7 in each arch). Each tooth surface is divided into 3 areas; three scores are recorded facially (mesiofacial, facial, distofacial) and three scores lingually (mesiolingual, lingual and distolingual), generating six scores per tooth.

The TPI scoring system is described in [Table 4-3](#).

Table 4-3 Turesky Plaque Index

Score	Description
0	No plaque
1	Separate flecks of plaque at the cervical margin of the tooth
2	Thin continuous band of plaque (1 millimetre (mm) or smaller) at the cervical margin of the tooth
3	Band of plaque wider than 1mm but covering less than 1/3 of the area
4	Plaque covering at least 1/3 but less than 2/3 of the area
5	Plaque covering 2/3 or more of the crown of the tooth
9	Missing tooth or not qualified tooth

Descriptive statistics (n, mean, SD, SE, median, minimum, maximum) will be presented for the Mean Overall TPI score and Mean Interproximal TPI score at each time point (observed value and change from baseline) by study product group for the mITT population in Table 14.2.5.1.1 and Table 14.2.6.1.1, respectively.

Raw means (\pm SE) of the Mean Overall TPI score and Mean Interproximal TPI score at each time point will be presented graphically by study product group in Figure 14.2.5.1.2 and Figure 14.2.6.1.2 respectively, for the mITT population.

Individual data for the TPI assessment at each evaluable tooth site will be listed for each subject by study product group in Listing 16.2.6.4.1, and individual data for the derived TPI score (overall and interproximal, respectively), will be listed for each subject in Listing 16.2.6.4.2, by study product group for all randomized subjects.

4.4.2.3.1 Statistical Hypothesis, Model and Method of Analysis

The following null and alternative hypotheses will be evaluated:

- **Overall TPI:**
 - H_0 : There is no difference in the mean Overall TPI score at 4 weeks between the Test product and Reference product.
 - H_1 : There is a difference in the mean Overall TPI score at 4 weeks between the Test product and Reference product.
- **Interproximal TPI:**
 - H_0 : There is no difference in the mean Interproximal TPI score at 4 weeks between the Test product and Reference product.
 - H_1 : There is a difference in the mean Interproximal TPI score at 4 weeks between the Test product and Reference product.

Mean Overall and Interproximal TPI will be analyzed as described for the primary analysis (Section 4.4.1.2), using the Baseline mean Overall/Interproximal TPI value as covariate, respectively. The adjusted means and SEs of the two product groups together with the product difference, SE, 95% CI of the difference and p-value will be provided in Table 14.2.5.2.1 and

Table 14.2.6.2.1 for the mITT population, respectively for Overall TPI and Interproximal TPI. The % adjusted mean difference will also be presented.

4.4.3 Exploratory Efficacy Variables

4.4.3.1 CCI

CCI

- Day 1 post-brushing compared to Day 1 pre-brushing
- Week 4 post-brushing compared to Week 4 pre-brushing
- Week 4 pre-brushing compared to Day 1 pre-brushing
- Week 4 post-brushing compared to Day 1 pre-brushing

Note: post-brushing is 3 hours post-brushing on site.

CCI

Descriptive statistics (n, mean, SD, SE, median, minimum, maximum) of CCI values at both the visits pre-brushing & post-brushing will be provided by study product group for the mITT population in Table 14.2.7.1.1.

Descriptive statistics (n, mean, SD, SE, median, minimum, maximum) CCI values at all the comparison of interest timepoints will be provided by study product group for the mITT population in Table 14.2.7.1.2.

Individual data CCI will be listed for each subject by visit with pre-brushing & post-brushing timepoint in Listing 16.2.6.5.

4.4.3.1.1 Statistical Hypothesis, Model and Method of Analysis

For comparisons within each treatment group, the following null and alternative hypotheses will be evaluated:

- CCI

• CCI

For comparisons to negative control, the following null and alternative hypotheses will be evaluated:

• CCI

CCI

For within treatment differences, the above time points will be analyzed using a paired t-test in Table 14.2.7.2.1.

CCI

CCI [REDACTED]. Subject will be included as a repeated measure with unstructured covariance matrix. Kenward Rogers degrees of freedom approach will be applied ([Kenward and Roger 1997](#)). The difference between the least square mean changes from timepoint x to timepoint y (where x represents the later timepoint and y represents the earlier timepoint in each comparison) for the Test Product compared to Reference Product (Negative Control) from the MMRM will be presented, along with the two-sided p-value and 95% CIs in table 14.2.7.2.2. The % adjusted mean difference will also be presented.

The assumptions of normality and homogeneity of variance in the MMRM will be investigated. Similarly, the assumptions for the paired t-test will be investigated. In case of violation of these assumptions, a van Elteren test adjusting for gender and baseline MGI stratification (between products comparisons) and Wilcoxon Signed Rank Test (within product comparisons with baseline) will be performed to support the parametric results.

4.4.4 Handling of Missing Values/Censoring/Discontinuations

Primary and Secondary Analysis:

Subjects who withdraw from the study early will be included in the statistical analysis up to the point at which they withdraw. There will be no imputation for missing data (i.e. analyses will be conducted on an observed case basis).

Exploratory Analysis:

CCI

4.5 Analysis of Safety

The safety profile of the study products will be assessed with respect to adverse events (AEs), and OST/OHT abnormalities in this oral health study.

4.5.1 Adverse Events and Serious Adverse Events

All AEs will be reviewed by the Clinical Research Scientist or designee prior to database lock and unblinding, and will be coded to a system organ class (SOC) and preferred term (PT) using the Medical Dictionary for Regulatory Activities (MedDRA).

AEs will be classified as oral and non-oral on the AE page of eCRF.

Treatment emergent adverse events (TEAEs) are defined as new AEs that occur on or after the first study product use (if this date is missing, a suitable alternative will be used e.g. date of randomization). AEs with an onset date/time prior to the first study product use at the baseline visit will be considered as non-treatment emergent.

The following summary tables and listings will be presented by study product group.

- Table of TEAEs overall summary (Table 14.3.1.1)
- Table of TEAEs by SOC and PT (Table 14.3.1.2)
- Table of TEAEs by Oral/Non-Oral and PT (Table 14.3.1.3)
- Table of treatment related TEAEs by SOC and PT (Table 14.3.1.4)
- Table of treatment related TEAEs by Oral/Non-Oral and PT (Table 14.3.1.5)
- Listing of all AEs (Listing 16.2.7.1 for all randomized subjects; Listing 16.2.7.2 for non-randomized subjects)
- Listing of deaths (Listing 14.3.2.1)
- Listing of non-fatal SAEs (Listing 14.3.2.2)
- Listing of TEAEs leading to study or product withdrawal (Listing 14.3.2.3)
- Listing of TEAEs classified as Oral (Listing 14.3.2.4)

In the event that there is nothing to report, a null table or listing will be produced.

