**CCI**

Within approximately 3-5 weeks (21-35 days) of Screening (Visit 1), eligible subjects will return to the site for the Baseline visit (Visit 2), with overnight plaque (subjects will be instructed to abstain from oral hygiene for 12 hours [+3 hours; -2 hours] i.e., overnight immediately before the visit). At the Baseline visit, concomitant medication and inclusion/exclusion criteria will be checked and then subjects will undergo a full OST examination, **CCI**, MGI, BI and TPI assessments.

Subjects will be considered eligible with a minimum of 20 natural teeth, at least 40 evaluable surfaces, overall  $MGI \geq 1.75$  and  $\leq 2.3$  and overall  $TPI \geq 1.5$ . Subjects with MGI and TPI score outside the study range will be discontinued from the study at this visit.

After **CCI** all initial clinical assessments, eligible subjects will receive a standardise snack followed by a full mouth dental prophylaxis to remove sub and supragingival calculus, stain, plaque and debris from the teeth. Post-prophylaxis, the subject's teeth will be re-disclosed, and a second clinician will check all plaque and calculus has been

Property of Haleon- Confidential

May not be used, divulged, published or otherwise disclosed without the consent of Haleon

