**Footnotes:**

1. In relation to the general dentition inclusion/ exclusion criteria
2. Subjects will abstain from overnight toothbrushing for a minimum of 12hrs (+3hr, -2hr) immediately prior to the assessment visits (Visits 2-3)
3. At least 3 subjects at each of visits 2&3 will be selected for repeat MGI assessments.
4. At least 3 subjects at each of visits 2&3 will be selected for repeat TPI assessments.
5. Adverse Events (AEs) and therefore all Serious Adverse Events (SAEs) will be collected immediately after a subject provides consent to participate in the study by the completion of the Informed Consent Form (ICF).

*The site may contact subjects prior to study visits, either as part of pre-screening activities or as a reminder of the approaching scheduled visit. Further details included in the ICF.*

Property of Haleon- Confidential

May not be used, divulged, published or otherwise disclosed without the consent of Haleon

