### **8.3.3 Safety Analysis(es)**

Safety analyses will be performed on the Safety population, according to investigational product received. AEs will be regarded as 'treatment emergent' if they occur on or after the first use of investigational product at Baseline. In the event of a missing start date, an AE will be assumed to be 'treatment emergent' unless the end date is prior to starting treatment. In case of misallocation, compared to the randomization schedule, TEAEs will be associated with the most recent study investigational received.

Property of Haleon- Confidential

May not be used, divulged, published or otherwise disclosed without the consent of Haleon

CCI

Abbreviated Clinical Protocol Template v1.0

Page 37 of 53

Haleon

Clinical Protocol

Protocol Number: 300178

Each AE will be categorized as oral or non-oral by the investigator or medically qualified designee. All will be reviewed by the CRS and coded using the MedDRA prior to database lock and unblinding.

A listing of all AEs will be presented for all subjects in the Safety population with the following AE summaries (number of distinct AEs and frequency/proportion of subjects affected) presented by treatment group and overall:

- TEAEs
- TEAEs by System Organ Class (SOC) and Preferred Term (PT)
- TEAEs by Oral/Non-Oral and PT
- Treatment emergent treatment related AEs by Oral/Non-Oral and PT
- Treatment emergent treatment related serious AEs by SOC and PT

Separate listings will be presented for:

- Deaths, SAEs and any AEs leading to product or study discontinuation.
- OST findings (with a summary of abnormalities by visit)

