## 9.2 Definition of an AE

An AE is any untoward medical occurrence in a clinical study subject, temporally associated with the use of a study product including any washout or lead-in product (or medical device), whether or not considered related to the study product, including any washout or lead-in product (or medical device).

NOTE: An AE can therefore be any unfavorable and unintended sign (including an abnormal laboratory finding), symptom, or disease (new or exacerbated) temporally associated with the use of a study product including any washout or lead-in product (or medical device).

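### SAP 4.5.1 has no provision for worsening, so an adverse event open at first brushing that intensifies on product and stays under its existing record is left out of every TEAE table

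*SAP*

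**What the plan says.** **SAP 4.5.1.** TEAEs "are defined as new AEs that occur on or after the first study product use". The next sentence closes the other side: "AEs with an onset date/time prior to the first study product use at the baseline visit will be considered as non-treatment emergent". Neither sentence mentions a rise in intensity.

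**Protocol 8.3.3.** "AEs will be regarded as 'treatment emergent' if they occur on or after the first use of investigational product at Baseline". This has no worsening clause either, but it does not contain the word *new*. SAP Table 5-1, which logs departures from the protocol's analysis, does not list that difference.

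**What counts as an AE.** Protocol 9.2 includes any "symptom, or disease (new or exacerbated) temporally associated with the use of a study product". Protocol 6.3.1 and 6.3.2 require a soft- or hard-tissue finding that has worsened since Screening to be recorded as an AE.

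**How changes are recorded.** Protocol 9.6 says only that updates go onto the AE page of the eCRF (and the SAE form where relevant). Protocol 9.5.1 gives each AE one intensity category.

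**The concern.** The only safety endpoint is TEAEs over 4 weeks, and the objective behind it is safety and oral tolerability. Aggravation of existing gingival or mucosal irritation is one of the ways in which a toothpaste could be poorly tolerated. A definition that looks only at the onset date classes such an event as non-treatment emergent whatever happens to it on product, provided that it keeps its existing record.

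The design makes this possible. AEs are collected from consent, the lead-in lasts weeks, and on Day 1 the gingival probing, plaque disclosure and full-mouth prophylaxis all come before the first supervised brushing. If such an event worsens on product, the by-arm TEAE summaries will not show it. Whether it is counted depends on how the site happens to record it.

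**Working it through.** The plan states no figure on this point, so the check is a reading of the passages together.

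**1. Can an AE be open at first brushing?** Yes. AEs "will be collected immediately after a subject provides consent to participate in the study" (Protocol Table 5-1 footnotes). The interval before product is long: "Within approximately 3-5 weeks (21-35 days) of Screening (Visit 1), eligible subjects will return to the site for the Baseline visit" (Protocol 3). In the Visit 2 order in Protocol 5.3, the BI assessment, disclosure and prophylaxis precede randomization and supervised brushing.

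**2. How is it classified if it worsens?** Take a hypothetical sore gingiva that starts after the prophylaxis, is mild at first brushing, and becomes moderate before Week 4.

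- *Kept under its existing record:* the onset date/time precedes first use, so the second sentence of the SAP rule makes it non-treatment emergent. The later intensity plays no part.
- *Worsening entered as a separate AE with its own start date:* that record is a new AE after first use and is a TEAE under the SAP as written.

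**3. Which of these do the documents require?** Neither. Protocol 9.2, 6.3.1 and 6.3.2 are consistent with a separate entry. Protocol 9.6 is at least as consistent with updating the existing entry. No passage tells the site to close an open AE and re-enter it with a new onset date.

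**4. Where would the single-record case appear?**

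| Display | Shown? |
|---|---|
| Tables 14.3.1.1 to 14.3.1.5 (all TEAE tables) | No |
| Listing 14.3.2.3 (TEAEs leading to withdrawal) | No |
| Listing 14.3.2.4 (oral TEAEs) | No |
| Listings 14.3.2.1 and 14.3.2.2 (deaths, non-fatal SAEs) | Yes, if fatal or serious |
| Listing 16.2.7.1 (all AEs, randomized subjects) | Yes |
| Table 14.3.4.1 (soft-tissue abnormalities by visit and product) | Only if visible at the examination; ungraded |

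On the withdrawal listing, Protocol 8.3.3 asks for any AE leading to discontinuation, whereas SAP Listing 14.3.2.3 is limited to TEAEs.

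**5. Size.** The documents give no rate of AEs open at first brushing and no rate of worsening. As assumptions only, let a share *p* of the 160 randomized subjects have an open AE and a share *w* of those worsen on product under one record. The number left out is 160 × *p* × *w*:

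- *p* = 5%, *w* = 5%: 160 × 0.05 × 0.05 = 0.4
- *p* = 10%, *w* = 10%: 160 × 0.10 × 0.10 = 1.6
- *p* = 20%, *w* = 30%: 160 × 0.20 × 0.30 = 9.6

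That is about 0.4 to 10 subjects in total, or 0.2 to 5 per arm if shared equally. The range only shows the scale and is not an estimate.

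**The case against.** The strongest reply is that the protocol already treats an exacerbation as an AE and requires worsened tissue findings to be recorded. A site that follows this and enters the worsening separately produces a TEAE, with no change to the SAP. The eCRF completion guidance is not among the documents and may already say so. This stands as a limit on the point: the omission arises only where the worsening is kept under the existing record. It does not remove the point, because nothing in the protocol or SAP settles the practice.

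Second, Table 14.3.4.1 compares soft-tissue abnormalities by arm at each visit, whatever the AE onset date. That also stands in part. The Baseline soft-tissue examination comes before probing and prophylaxis, so irritation from those procedures that is still visible at Week 4 would be counted. But the table does not grade severity, misses lesions that have resolved, and cannot show pain or sensitivity without a visible finding. Hard-tissue findings are only listed.

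Third, Protocol 8.3.3 has no worsening clause, so the SAP largely follows the protocol's own onset-based approach. This is fair. The SAP's added word *new* is an unlogged narrowing, but not a plain contradiction.

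Fourth, few subjects are likely to be involved and no safety hypothesis is tested. Both are true, and they limit the weight of the point.

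**Conclusion.** The point holds in a conditional form. An AE already open at first brushing that worsens on product, and is kept under one record, is left out of all five TEAE tables and the two TEAE-only listings. It remains in the all-AE listing, in the death or SAE listings if serious, and possibly, ungraded, in the soft-tissue table. The number affected is unknown and probably small, and the primary analysis is not touched. The change is worth making because the rule misclassifies events for the only safety endpoint and costs little to correct.

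A reader might infer more than the documents support:

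- *That worsening can never reach a TEAE table.* It can, if entered as a separate AE.
- *That such events appear only in listings.* Table 14.3.4.1 gives a partial by-arm view of soft-tissue findings.
- *That a definite number of events will be missed.* Any figure rests wholly on assumed rates.
- *That the SAP has dropped the rule for a missing AE start date.* Protocol 8.3.3 presumes such an AE treatment-emergent "unless the end date is prior to starting treatment". The SAP does not repeat this, but its exclusion needs a known earlier onset, so it does not contradict the rule. Copying it across would be tidying.

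**What to change.** 1. In SAP 4.5.1, define a TEAE as an AE with onset on or after first product use, or an AE with earlier onset that increases in intensity or becomes serious on or after first use.
2. Record this in SAP Table 5-1 as a change from Protocol 8.3.3.
3. Set one recording convention: the worsening is entered as a new AE record with its own start date, linked to the existing one. This suits Protocol 9.5.1, which assigns one intensity per AE and so gives no history of intensity within a record.
4. State that each worsening is counted once, through the new record. Without this, the wider definition and the new record together could count one worsening twice in the number of distinct AEs.

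AE records already entered can be checked against the convention during the AE review that SAP 4.5.1 places before database lock and unblinding.

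The cost is a few sentences in the SAP and one line of site guidance. The small downside is that a few more TEAEs will be reported in both arms.

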4.5.2 Other Safety Variables

Other safety variables are listed below:

- OST examination
- OHT examination

4.5.2.1 OST Examination

The OST examination will be accomplished by direct observation and palpation, using retraction aids as appropriate. It will include examination of the labial mucosa (including lips), buccal mucosa, mucogingival folds, gingival mucosa, hard palate, soft palate, tonsillar area, pharyngeal area, tongue, sublingual area, submandibular area and salivary glands. Any abnormal findings from the OST examination will be recorded in the eCRF with details of the abnormalities.

Where possible, this procedure should be conducted by a single clinical examiner.

OST will be summarized (number of subjects and percentages with abnormalities) by visit and study product in Table 14.3.4.1 for all subjects in the Safety Population. Abnormal findings from the OST examination will be listed (Listing 16.2.8.1) for all randomized subjects.

4.5.2.2 OHT Examination

The OHT examination will be accomplished by direct observation, using retraction aids as appropriate. It will identify enamel irregularities, tooth fractures, grossly carious lesions/gross decay, defective/faulty restorations, direct & indirect restorations including fixed/removal prostheses, non-carious tooth surface loss (abrasion, attrition, abfraction and erosion), any other hard tissue irregularities (e.g., hypo/hypermineralisation, decalcification) and significant tooth staining. Any conditions noted as 'Present' from the OHT examination will be described in the eCRF with details of the 'Present' condition.

The presence of implants, fixed or removable dentures, fixed or removable orthodontic braces/bands, fixed orthodontic retainers, full crowns or veneers will be recorded, along with evidence of gross intra-oral neglect or the need for extensive dental therapy. Where possible, this procedure should be conducted by a single clinical examiner.

Any conditions noted as 'Present' from the OHT examination will be listed (Listing 16.2.8.2) for all randomized subjects.

4.6 Analysis of Other Variables

4.6.1 Repeatability of the Examiner

Repeat MGI and TPI assessments will be performed by the clinical examiners at Visits 2 and 3. At least 3 subjects will be selected for repeat assessments over the duration of each of visits 2 and 3. Thus a total of at least 6 subjects repeat assessments for each endpoint will be collected during this study. 'Repeat' subjects will be selected at random from those in attendance on any given assessment day. Different subjects should be used for repeat MGI and TPI assessments.

There should be a delay of at least 10 minutes between the original and the repeat assessment for a given subject; ideally, repeat assessments should be separated by another subject. No other clinical procedure should be carried out on the selected subject between repeat assessments.

Scores from the first assessment must not be visible to the examiner/scribe when the repeat assessment is carried out.

The repeat MGI and TPI assessments will be compared to the respective original assessments (excluding any tooth surfaces assessed as missing or not qualified). The repeat assessments will not be used in any efficacy analysis.

The first and second assessments of each index will be analyzed with a Fleiss-Cohen weighted kappa coefficient (κ), along with the 95% CI, to assess the intra-examiner reliability. Reliability will be deemed:

- Excellent if $\kappa > 0.75$

- Fair to good if $0.4 \leq \kappa \leq 0.75$
- Poor if $\kappa < 0.4$

This analysis will be conducted on each respective index repeatability population (MGI population and TPI population).

